Probiotics also found to have an effect in inducing, maintaining and increasing the remission period in UC and this effect suggested to be also associated with the immunomodulator role of certain microorganisms (Tamaki *et al.* 2016). For example, *in vitro* studies, *Lactobacillus casei* strain Shirota found to have anti-inflammatory effect by inhibition of IL-6 and interferon c (IFN-c) synthesis in lipopolysaccharide (LPS)-stimulated murine chronic IBD cells (Matsumoto *et al.* 2005), and *Lactobacillus delbrueckii* had anti-inflammatory effect by inhibition of NF- κ B pathway in large intestinal lamina propria mononuclear cells (Santos Rocha *et al.* 2012). *In vivo*, *Lactobacillus delbrueckii* and *Lactobacillus fermentum* supplementation, in UC patients undergoing treatment with sulfasalazine (an anti-inflammatory medicine) showed a reduction in several pro-inflammatory parameters in the colon, such as IL-6 levels, tumor necrosis factor TNF- α and NF- κ B p65 expression, and leukocyte recruitment, in comparison with the placebo and medical treatment groups (Hegazy and El-Bedewy 2010). In another study where *Bifidobacterium breve* was administrated as a part of a symbiotic, the results showed a significant decrease in the inflammatory parameters and improvement in the clinical status evaluated by colonoscopy in patients with mild to moderate UC (Ishikawa *et al.* 2011). Moreover, administration of probiotic product Bifid Triple Viable, that contains *Lactobacillus acidophilus*, *B. bifidum* and *Streptococcus*, for 2 months, lead to reduce the expression of IL-1b and increased the expression of IL-10 and immunoglobulin A (IgA) in the colon of UC patients (Li *et al.* 2012).

Materials and Methods:

Study Design

An interventional double-blind randomized controlled trial (RCT) design will be used in this study. A placebo group will be included parallel with the treatment group in this study. Forty IBD patients with mild to moderately active UC aged 18-65 will be recruited conveniently from the gastroenterology section, the IBD clinic at the Jordan University Hospital and Al-Bashir Hospital, Amman, Jordan. Patients who meet the inclusion criteria and agree to participate will be centrally

randomized to probiotic supplementation group or placebo group using computer-generated

random numbers, stratified by age and gender. The duration of intervention will be 6 weeks. **The**

study scheme:

The Interventions

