Palumbo *et al.*, 2016.

Ethical Approval:

This study will seek approval by Research Ethics Committee at the University of Jordan and by the Institution Research Board (IRB) of Jordan University Hospital and Al-Bashir Hospital, Amman, Jordan. The participants will be provided with information consent containing a brief description of the study and written informed consent will be obtained from all participants before their interview and blood drawl (10ml) (Appendix 1, 2). Participants' information will be treated confidentially. However, only the researcher (PhD student) will know participants' names and she is the only one who will give them identification (ID) number.

Personal Questionnaire:

The personal questionnaire will contain questions related to age, gender, education, employment, family income/month, residency area, smoking status, family history of IBD, medications, previous and current health problems. As well as, questions about using probiotics and certain eating habits will be asked (Appendix3). Anthropometric measurements including weight (measured to the nearest 0.1 kilogram) and height (measured to the nearest 1 cm) will be taken from the existing medical record. Body mass index (BMI) will be calculated.

Biochemical Measurements:

The researcher will take the permission form the participants to draw blood sample (10ml) and perform biochemical specialized labs. Venous blood samples will be withdrawn by specialized medical laboratory technicians. Complete blood count (CBC) will be analyzed using standard procedure. Blood serum will be separated by centrifugation (3000 rpm for 10 min) after clotting at room temperature (27 °C) and stored at -18°C until analysis. Immunoglobulin G(IgG), Immunoglobulin M (IgM), Immunoglobulin (IgA), interleukin (IL)-6, IL-1, IL-10, C-Reactive Protein (CRP), and TNF- α will be analyzed using commercially available enzyme-linked immunosorbent assay (ELISA) kits.

Data Collection and Quality of Life Questionnaire

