Three parts package was used for collecting data that met the purpose of this study, including a personal questionnaire, physical activity questionnaire, and a short inflammatory bowel disease questionnaire (SIBDQ). A face-to-face interview technique was used as a method for data collection. Data on age, body weight, educational level, previous and current health problems, family history of IBD, and probiotic use were collected. The physical activity level was measured using a 7-day Physical Activity Recall (PAR) which was originally developed by Sallis *et al.*, 1985 (Sallis *et al.*, 1985). For assessing the quality of life, a disease-specific, validated, and reliable Arabic version of the SIBDQ obtained from the McMaster short IBD questionnaire at McMaster University was used (Mahalli and Alharthi, 2017). The SIBDQ contains ten questions covering the four HRQOL domains (systemic, social, bowel, and emotional) which were calculated and scored. The response to each question of the ten was graded on a 7-point Likert scale ranging from 1 (worst aspect) to 7 (best aspect). The total SIBDQ scores range from 10 to 70, with higher scores indicating better HRQOL (Mahalli and Alharthi, 2017). The summation of the responses to Q4, Q6, and Q9 was used for the bowel domain, the sum of the responses to Q2 and Q3 was for the social domain, the sum of the responses to Q1 and Q7 was for the systemic domain, and the sum of the responses to Q5, Q8, and Q10 was for the emotional domain. The total score of SIBDQ was composed of the sum of the responses to all ten questions (Guyatt *et al.*, 1989; Mahalli and Alharthi, 2017).

Statistical Analysis:

Statistical analysis will be done using IBM SPSS Statistics 20.0 software (version 20.0, IBM, Inc., Chicago, IL, USA). Mean \pm standard deviation (SD) will be used to express the continuous data and percentage to express the categorical data. The categorical variables will be compared using the Chi square and the continuous variables will be compared using the one-way ANOVA. A

paired *t*-test will be used to assess within-group changes in outcomes from baseline to end of intervention. For all data, *P*< 0.05 will be considered statistically significant.

References

Abraham, B. P., and Quigley, E. M. (2017), Probiotics in inflammatory bowel disease. **Gastroenterology Clinics**, 46(4), 769-782.

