Effect Of Probiotic Supplementation on The Immune System in Patients with Ulcerative Colitis in Amman, Jordan

By

[name]

Supervisor

[name] [name]

Co-Supervisor

[name] [name]

Funded by the University of Jordan

22 November 2023

NCT04223479

Statistical Analysis

Statistical analyses were performed using Statistical Package for Social Science (IBM® SPSS® Statistics; Version 21.0, version for Windows, 2019, USA). Mean and standard deviation (SD) were calculated for the continuous variables. Frequencies and percentages were used to describe categorical variables. The frequency of participants in terms of categorical variables was compared using the X² test. To check the normal distribution of continuous variables, the Shapiro-Wilk test was applied. Independent samples T-test was used to detect differences between placebo and probiotics groups in terms of continuous variables. A paired t-test was used to assess withingroup changes in biochemical parameters (IgG, IgM, IgA, IL-1, IL-6, IL10, TNF-α, and CRP) from baseline to the end of the study. A p-value < 0.05 was considered statistically significant. All outcomes were calculated by intention-to-treat (ITT) and perprotocol (PP) analyses. For ITT analysis, all randomized patients who took at least one tablet of study medication were included. For PP analysis all protocol violators (patients' dropout or loss of follow-up) were excluded.

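### Two hospitals recruit the 40 patients, but the between-arm comparison has no hospital term; adding one is a cheap guard against noise and chance imbalance

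*Protocol*

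**What the plan says.** The protocol's Study Design section recruits "Forty IBD patients with mild to moderately active UC aged 18-65" by convenience from "the IBD clinic at the Jordan University Hospital and Al-Bashir Hospital, Amman, Jordan". The Ethical Approval section confirms two institutions, seeking approval from the "Institution Research Board (IRB) of Jordan University Hospital and Al-Bashir Hospital, Amman, Jordan".

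Allocation is central and uses computer-generated "random numbers, stratified by age and gender". Hospital is not listed as a factor.

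For the comparison between arms, the protocol's Statistical Analysis section says "the continuous variables will be compared using the one-way ANOVA", and the SAP says "Independent samples T-test was used to detect differences between placebo and probiotics groups in terms of continuous variables". Within arms, the SAP states: "A paired t-test was used to assess withingroup changes in biochemical parameters". Neither document contains a hospital term, a stratified analysis or any other covariate.

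On blood handling, the Biochemical Measurements section says "Venous blood samples will be withdrawn by specialized medical laboratory technicians". It then gives a single procedure for clotting, centrifugation, storage and ELISA. It does not say whether one laboratory processes the samples from both hospitals.

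**The concern.** Hospital is known for every patient when allocation takes place, yet the plan uses it neither there nor in the analysis. Recruitment is by convenience, so nothing aligns the case mix of the two clinics. If marker levels or SIBDQ scores differ between the hospitals for any reason, two things follow. The difference sits in the error term of the t-test or ANOVA and widens the confidence interval. And in the one allocation this trial gets, an uneven split of hospitals across arms carries part of that difference into the estimated treatment effect.

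Precision is scarce here. The documents give no power calculation, and 20 per arm can reliably detect only a large effect (about 0.9 SD for 80% power, two-sided 5%).

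**Working it through.** The plan gives no power, SD or between-hospital figure, so there is nothing to reproduce.

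**Inputs.** From the documents: 40 patients, two hospitals, strata of age and gender, no hospital term. Assumed: 1:1 allocation (20 per arm), a 20:20 hospital split, allocation independent of hospital, and a hospital gap δ of 0, 0.5 or 1 within-hospital SD in the analysed value. The documents supply no value for δ.

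**1. Chance of an uneven split.** The number of one hospital's 20 patients who land in the probiotic arm is hypergeometric: P(x) = C(20,x)·C(20,20−x)/C(40,20).

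- P(10) = 0.248; P(9) = P(11) = 0.205; P(8) = P(12) = 0.115.
- 12:8 or worse: 1 − 0.248 − 2(0.205) = 0.34.
- 13:7 or worse: 0.343 − 2(0.115) = 0.11.

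**2. Noise and shift.** With a proportion p of patients from one hospital, omitting hospital multiplies the variance by 1 + p(1−p)δ², which is 1 + 0.25δ² at 20:20. The share of variance due to hospital is R² = 0.25δ²/(1 + 0.25δ²). The patients lost are 40(1 − 1/inflation). An a:b split shifts the arm difference by δ(a−b)/20.

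| Gap δ | Variance inflation | R² | Patients lost of 40 | Shift at 12:8 | Shift at 13:7 |
|---|---|---|---|---|---|
| 0 | 1.00 | 0% | 0 | 0 | 0 |
| 0.5 SD | 1.06 | 6% | about 2 | 0.10 SD | 0.15 SD |
| 1 SD | 1.25 | 20% | 8 | 0.20 SD | 0.30 SD |

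For scale, the standard error of the arm difference with 20 per arm is √(2/20) = 0.32 SD when the hospitals do not differ.

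**3. Sensitivity to the hospital split.** 20:20 is the least favourable case. At 30:10, p(1−p) = 0.1875, so the inflation is 5% at 0.5 SD and 19% at 1 SD. The chance that the arms differ by 4 or more patients from one hospital falls from 34% to 27%, and by 6 or more from 11% to 6.5%.

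**4. What a hospital term would change.** Take the effect at which the unadjusted t-test has 80% power (0.91 SD by the exact t calculation), and add hospital in the analysis only, without stratifying on it:

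| R² due to hospital | Power with hospital term |
|---|---|
| 0% | 78.9% |
| 2% | 79.5% |
| 5% | 80.7% |
| 10% | 82.9% |
| 20% | 87.0% |

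The term costs about one power point if hospital explains nothing and half a point at 2%. It roughly breaks even by 5% and gains about seven points at 20%.

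**The case against.** The strongest reply is that nothing in the plan is invalid. Central computer-generated randomisation gives an unbiased comparison whether or not hospital is a stratum. When allocation ignores hospital, the larger error term already allows for chance imbalance. The 13:7 shift is therefore one instance of the inflated variance and should not be counted as a second harm. This stands. A reader might infer that the treatment comparison is biased by site; the documents do not support that.

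A reader might also infer that care, disease grading or blood handling differs between the hospitals. The documents do not show this either. The protocol describes one blood-handling procedure, both hospitals are in Amman, and the same entry criteria apply. The MMDAI defines eligibility and is not an analysed outcome, so differences between graders could act only through case mix. What the documents leave open is whether one laboratory was used.

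A stable difference in level between hospitals would cancel in a change from baseline. This is correct, but the SAP does not say whether the between-arm t-test compares changes or end values. A hospital difference in six-week change would not cancel in either case.

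Finally, the size is uncertain. A 1 SD gap at a 20:20 split is near the upper end, and at a gap of about 0.5 SD or less the gain is small. That limits the importance of the point without removing it, because the cost of adjusting is smaller still.

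**Conclusion.** The point holds as a minor, inexpensive improvement in precision. Recruiting hospital is known for every patient but appears in neither the randomisation strata nor the between-arm analysis. Under the assumed 20:20 split, omitting it costs between nothing (no gap) and the equivalent of 8 of 40 patients (1 SD gap), with about 2 patients at 0.5 SD. The chance of a 13:7 or worse split is 11%, and the estimate then moves by at least 0.15 SD at a 0.5 SD gap or 0.30 SD at 1 SD. All of this rests on an assumed hospital gap, equal arms and equal hospitals, none of which the documents give.

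A reader might conclude that hospital should have been a third stratum or should have replaced age. The documents do not support that. Three factors with two levels each give at least 8 cells averaging 5 patients, and the protocol's literature review names age, not hospital, as a risk factor for UC. The SAP is also written in the past tense, so allocation is probably complete.

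**What to change.** For the blood markers and the SIBDQ, fit the between-arm comparison as a linear model with arm, baseline value and hospital as a fixed term. State whether the analysed value is the end value or the change; with baseline in the model, the estimated arm effect is the same for both. Report how many patients from each hospital were in each arm, and say whether one laboratory handled all samples.

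If the between-arm analysis has already been run, keep the planned test as reported and present the hospital-adjusted model as a labelled sensitivity analysis, since choosing it afterwards as the main result would be post hoc. Leave the randomisation strata as they are.

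The hospital term costs one degree of freedom and about one power point or less if hospital explains almost no variance. It needs no data beyond the recruiting hospital.

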probiotic-derived ferrichrome, or activation of natural killer cells (Hu *et al.*, 2015; Cai *et al.*, 2016; Konishi *et al.*, 2016; Dargahi *et al.*, 2019). Additionally, Lactobacillus mixture shifted the gut microbial community toward *Prevotella* and *Oscillibacter*, which are known to produce anti-inflammatory metabolites that decrease Th17 polarization and enhance the differentiation of anti-inflammatory Treg/Tr1 cells in the gut (Li *et al.*, 2016; Dargahi *et al.*, 2019).

Probiotics Role in Ulcerative Colitis

The uses of probiotics for UC have been explored under a variety of experimental conditions both in vitro and in vivo (Abraham and Quigley 2017; Guandalini and Sansotta, 2019). Studies revealed that using of probiotics as an adjunct to medical therapy might be useful in the treatment of UC (Shen *et al.*, 2018; Guandalini and Sansotta, 2019). This beneficial effect of Probiotics may be explained through at least two mechanisms (Witkowski *et al.*, 2018). First one, their ability to enhance the mucosal barrier function, which shown to promote the secretion of IgA and mucins (Kabeerdoss *et al.*, 2010) and tight junction function (Karczewski *et al.*, 2010; Kotzampassi and Gimarellos-Bourboulis, 2012). Secondly, through their interaction with the local immune system to enhance regulatory T cell responses, decreased the pro-inflammatory cytokines such as TNF- α and IL-1 β and increased anti-inflammatory factor IL-10 (de Moreno *et al.*, 2011; Zhao *et al.*, 2013), consequently improving the symptoms of UC, and this mediated through PI3K/Akt and NF-B signaling pathway (Shen *et al.*, 2018; Witkowski *et al.*, 2018). *Bifidobacterium* probiotic is one of beneficial microbiota that promotes antitumor immunity and prevents recurrence of UC (Ventura *et al.*, 2014). Anther probiotic that studied and used for treating UC are *E. coli Nissle* 1917, which widely used in Europe (Scaldaferri *et al.*, 2016), *Saccharomyces boulardii* (Thomas *et al.* 2011; Limketkai *et al.*, 2018) and lactic acid-producing bacteria (*L. plantarum*, *L. delbrueckii* subsp. *bulgaricus*, *L. casei*, *L. acidophilus*, *Bifidobacterium breve*, *B. longum*, *B. infantis*, *L. paracasei* subsp. *paracasei*, *Lactobacillus casei* strain *Shirota* and *Streptococcus salivarius* subsp. *Thermophilus*) (Limketkai *et al.*, 2018; Guandalini and Sansotta, 2019).

[figure not shown]

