The probiotics and placebo treatments will be given at weekly basis in double blind manner for the six weeks. The patients in the probiotics group will receive 3 oral viable capsules of Jamieson Probiotic 10 Billion product, each of which contain ($1*10^{10}$ CFU/g) of *lactobacillus* (*Lactobacillus rhamnosus* HA-111, *Lactobacillus acidophilus* HA-122, *Lactobacillus salivarius* HA-118, *Lactobacillus paracasei* HA-196) and *bifidobacterium* (*Bifidobacterium breve* HA-129, *Bifidobacterium bifidum* HA-132 HA, *Bifidobacterium longum* HA-135) species three times a day. Similarly, the placebo group will receive 3 placebo capsules containing maltodextrin three times a day.

Human Participants:

Inclusion and Exclusion Criteria:

Inclusion criteria will be patients with age between 18 -70 years and diagnosed with UC established by colonoscopy and histology, and suffering from mild to moderate UC as defined by Modified Mayo Disease Activity Index (MMDAI, table 1) (score 3–9), the diagnoses will be done by a physician (Ng *et al.*, 2010; Palumbo *et al.*, 2016; Tamaki *et al.* 2016). Patients will be excluded if they had age <18 years, >70 years, pregnancy, planned pregnancy, breastfeeding, evidence of severe disease (MMDAI >10), concurrent enteric infection, use of antibiotics within the past 2 weeks, change in dose of oral 5-aminosalicylic acid (5-ASA) within the past 4 weeks, and use of rectal 5-ASA or steroids within 7 days before entry into the study, or the use of probiotic preparations during study, received any investigational medicines within 3 months, and if they have significant hepatic, renal, endocrine, respiratory, neurological, or cardiovascular diseases were also excluded (Ng *et al.*, 2010; Bengtsson *et al.*, 2016; Tamaki *et al.* 2016; Palumbo *et al.*, 2016).

Table 1. Modified Mayo Disease Activity Index.

Grade	Bowel frequency	Rectal bleeding	Physician's global assessment	Endoscopy/sigmoidoscopy finding
0	Normal number of stools per day for this patient	No blood seen	Normal	Normal or inactive disease
1	1 or 2 more stools than normal	Streaks of blood with stool less than half the time	Mild disease	Mild disease (erythema, decreased vascular pattern)
2	3 or 4 more stools than normal	Obvious blood with stool most of the time	Moderate disease	Moderate disease (marked erythema, absent vascular pattern, friability, erosions)
3	5 or more stools than normal	Blood alone passed	Severe disease	Severe disease (spontaneous bleeding, ulceration)

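### Disease activity at entry is known before randomisation but is used in neither the stratification nor the between-arm analysis; adjusting for it would cost almost nothing

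*Protocol*

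**What the plan says.** **Allocation.** The protocol (Materials and Methods, Study Design) uses computer-generated "random numbers, stratified by age and gender". It gives no age bands and no reason for the two factors. The sample is stated without a calculation: "Forty IBD patients with mild to moderately active UC aged 18-65 will be recruited conveniently". The allocation ratio is not given.

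**Timing of the score.** Patients qualify if they are "suffering from mild to moderate UC as defined by Modified Mayo Disease Activity Index", with a score of 3 to 9 (Inclusion and Exclusion Criteria). Table 1 of the protocol has four items graded 0 to 3, so the maximum is 4 × 3 = 12. Randomisation follows eligibility: "Patients who meet the inclusion criteria and agree to participate will be centrally" randomised. Entry MMDAI therefore exists for everyone at allocation.

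**Analysis.** The protocol's Statistical Analysis section compares continuous variables between groups by one-way ANOVA. The SAP uses an independent-samples t-test. Neither includes MMDAI, the baseline value of the outcome, age or gender. Both add paired t-tests within each arm.

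**The concern.** The outcomes are CRP, cytokines, immunoglobulins and a disease-specific quality-of-life score in patients with active UC. An entry range of 3 to 9 on a 12-point scale leaves room for real differences in severity between patients.

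The protocol's background connects activity with these outcomes in general terms. It describes cytokine changes under probiotics as "consequently improving the symptoms of UC". It cites a study that found a "significant decrease in the inflammatory parameters and improvement in the clinical status evaluated by colonoscopy in patients with mild to moderate UC". It also attributes reduced quality of life to the symptoms of relapse.

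If entry activity does predict the outcomes, leaving it out of both design and analysis has two costs. A chance excess of moderate disease in one arm can move several related outcomes, and nothing in the plan corrects for it. Variance that the score could explain also stays in the error term, in a trial with few patients.

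**Working it through.** The documents give no power, effect size or SD, so there is no planned figure to reproduce. The inputs are N = 40 (protocol, Study Design) and p < 0.05 (both analysis sections). Assumed: 20 per arm, a two-sided test, a 0.8 SD effect, the share with moderate disease, and the correlation r between entry MMDAI and the outcome.

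**1. Chance imbalance.** If M of the 40 are moderate, the number X in one arm is hypergeometric (40, M, 20) and the gap between arms is |2X − M|.

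| M moderate | P(gap ≥ 4) | P(gap ≥ 6) |
|---|---|---|
| 12 | 30% | 8% |
| 16 | 33% | 11% |
| 17 | 20% | 5% |
| 19 | 20% | 6% |
| 20 | 34% | 11% |

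An odd M allows only odd gaps, so four or more then means five or more. For M from 16 to 24 the first column runs from 20% to 34%. It can be lower for more lopsided splits (18% at M = 13).

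In a simulation (10,000 trials; blocks of 4; two age bands; two genders; 50% moderate; all factors independent), a gap of 20 percentage points or more occurred in 26% of trials with no stratification and 24% with age by gender. Under these assumptions the planned strata do little to balance activity.

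**2. What an imbalance does to the unadjusted test.** The standardised MMDAI difference between arms has SD √(2/20) = 0.316, so P(|difference| > 0.5 SD) = 11%. A 0.5 SD imbalance shifts the comparison by 0.5r. Given that imbalance, the comparison has SD 0.316√(1 − r²), while the test still uses 0.316 (normal approximation):

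- r = 0.2: shift 0.10 SD, conditional type I error 5.7%
- r = 0.3: shift 0.15 SD, 6.5%
- r = 0.5: shift 0.25 SD, 8.9%

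Averaged over all allocations, the error rate stays at about 5%.

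**3. Gain from adjustment.** Adjustment multiplies the residual variance by 1 − r². Power comes from the noncentral t with 38 degrees of freedom and noncentrality (0.8/√(1 − r²)) × √(20/2).

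| r | 1 − r² | Noncentrality | Power | 40/(1 − r²) |
|---|---|---|---|---|
| 0 (unadjusted) | 1.00 | 2.530 | 69% | 40.0 |
| 0.1 | 0.99 | 2.543 | 70% | 40.4 |
| 0.2 | 0.96 | 2.582 | 71% | 41.7 |
| 0.3 | 0.91 | 2.652 | 73% | 44.0 |
| 0.4 | 0.84 | 2.760 | 77% | 47.6 |
| 0.5 | 0.75 | 2.921 | 81% | 53.3 |

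The last column is the unadjusted sample size that would give the same precision.

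**4. Stratification or adjustment?** Simulated power at 0.8 SD with a binary severity factor:

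| Design and analysis | r = 0.3 | r = 0.5 |
|---|---|---|
| Not stratified on activity, unadjusted | 69% | 69% |
| Stratified on activity, unadjusted | 70% | 72% |
| Not stratified on activity, adjusted | 72% | 80% |
| Stratified on activity, adjusted | 73-74% | 81% |

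Most of the gain comes from the model term. Stratifying on activity but keeping the unadjusted test makes that test conservative (type I error about 4.0% and 2.3%).

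**The case against.** The strongest reply is that nothing here is invalid. Age and gender are legitimate strata, randomisation protects the comparison on average, and a 5% test already allows for chance imbalance. That stands. A reader might infer that omitting MMDAI biases the trial, but the documents do not support this. The higher error rates in step 2 are conditional on an unlucky allocation.

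A reader might also infer that age was chosen with no connection to the disease. The protocol's section on risk factors lists age in a paragraph on the development and severity of UC, so age has an indirect link. No link is given for gender. Swapping age for MMDAI as a stratum is therefore a debatable trade.

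The link between entry MMDAI and the outcomes is equally unquantified. The background passages on cytokines and colonoscopic status describe changes under treatment, and none reports a correlation between entry score and a marker within the mild-to-moderate range. At r = 0.1-0.2 the gain is only one or two points of power.

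Nor can one say that an excess of moderate disease would push every outcome the same way. The protocol describes IL-10 as anti-inflammatory, and no document says how the immunoglobulins vary with severity.

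Finally, the SAP is written in the past tense, as is the protocol's data-collection section, so allocation is probably complete. That removes the practical case for new strata, but not the case for a covariate that has already been collected.

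**Conclusion.** The point holds as a low-priority improvement to the analysis. Entry MMDAI is available for every patient and used nowhere. The cost is an uncorrected chance imbalance (about 20-34% for a gap of four or more moderate patients, with 20 per arm and 16 to 24 moderate) and a possible loss of precision.

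At 0.8 SD, adjustment is worth one to two points of power if r is 0.1-0.2 and about 4 to 12 points if r is 0.3-0.5. The allocation ratio, effect size, share with moderate disease and correlations are all assumptions. The gain shrinks for an outcome that is also adjusted for its own baseline, and part of a baseline difference would already cancel if the t-test is applied to changes. The SAP does not say whether it uses final values or changes.

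A stronger reading, that the choice of strata is itself a defect to be corrected, is not supported. Step 4 shows that re-stratifying adds about one point once the analysis is adjusted and one to three points if it is not.

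**What to change.** Replace the unadjusted between-arm test with an ANCOVA for each continuous outcome. Include treatment, entry MMDAI as a continuous score, the baseline value of the outcome where it was measured, and the stratification factors age and gender. State the age bands used at randomisation. If anyone responsible for the analysis has already seen unblinded outcome data, present this model as a sensitivity analysis beside the planned test. In either case, report entry MMDAI by arm.

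The cost is one short paragraph in the SAP and no new data. Four covariates use four of the 38 residual degrees of freedom, leaving 34.

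Only if allocation has not begun could the strata also be reconsidered. Adding a two-level MMDAI factor to two age bands and gender would give eight cells averaging five patients. Replacing age would keep four cells averaging ten, but age would no longer be balanced by design. The documents define no cut between mild and moderate, so one would have to be specified. This step is optional and is not needed for most of the gain.

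### No look-back covers probiotic use before entry, and the protocol and SAP do not agree on how outside probiotic use after randomisation is handled

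*Protocol*

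**What the plan says.** The Protocol, under Inclusion and Exclusion Criteria, puts its exclusions in one sentence. For probiotics the only entry is "or the use of probiotic preparations during study". The other treatments in that sentence have a period that looks back from entry:

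- antibiotics: "use of antibiotics within the past 2 weeks"
- oral 5-ASA: "change in dose of oral 5-aminosalicylic acid (5-ASA) within the past 4 weeks"
- rectal 5-ASA or steroids: "use of rectal 5-ASA or steroids within 7 days before entry into the study"
- investigational products: "received any investigational medicines within 3 months"

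Under Personal Questionnaire the protocol adds that "questions about using probiotics and certain eating habits will be asked". The section on data collection and quality of life also lists probiotic use among the items collected. Neither place ties the answer to eligibility or to an analysis.

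The SAP defines the ITT set so that "all randomized patients who took at least one tablet of study medication were included". Its per-protocol set leaves out protocol violators, described in brackets only as dropout or loss to follow-up. It plans paired t-tests from baseline to end of study for IgG, IgM, IgA, IL-1, IL-6, IL-10, TNF-α and CRP, and independent-samples t-tests between the arms.

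**The concern.** The product under test is a probiotic, yet probiotics are the one listed treatment without a look-back. A patient who takes a probiotic until the day of baseline blood and stops on entry meets every written criterion.

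The protocol's own rationale is that probiotics lower TNF-α, IL-1β and IL-6 and raise IL-10 and IgA. Those markers, or their family in the case of IL-1, are the trial's outcomes. A recent user may therefore start with a baseline that the test class has already moved, and the SAP's paired tests take that baseline as their reference. If the earlier effect lasts to week 6 in placebo patients, the between-arm difference shrinks as well.

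A second gap concerns use after randomisation. If a placebo patient buys a probiotic in week 3, the exclusion list, the ITT definition and the per-protocol definition do not lead the analyst to one answer.

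**Working it through.** **1. The text, side by side**

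| Treatment | Period before entry |
|---|---|
| Antibiotics | 2 weeks |
| Oral 5-ASA dose change | 4 weeks |
| Rectal 5-ASA or steroids | 7 days |
| Investigational medicines | 3 months |
| Probiotics | none; only use during the study |

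| Outside probiotic use after randomisation | Handling |
|---|---|
| Protocol, exclusion list | listed as an exclusion |
| SAP, ITT set | patient kept after at least one tablet |
| SAP, per-protocol set | not named; only dropout or loss to follow-up |

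**2. Where prior use enters the analysis**

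Let δ be the full probiotic effect on a marker and p the share of recent users, equal in both arms in expectation because they are randomised. Let b be the share of δ already present in them at baseline, and k the share still present at week 6 in those given placebo. Assume that everyone on active capsules reaches δ at week 6.

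- Mean change, probiotic arm: δ − pbδ = δ(1 − pb)
- Mean change, placebo arm: pkδ − pbδ = −p(b − k)δ
- Difference in change: δ(1 − pb) + p(b − k)δ = δ(1 − pk)
- Difference at week 6: δ − pkδ = δ(1 − pk)

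Example with p = 20% and b = 1:

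| Carry-over at week 6 | Change, probiotic | Change, placebo | Between-arm contrast |
|---|---|---|---|
| k = 0 (cleared) | 0.8δ | −0.2δ | δ |
| k = 1 (full) | 0.8δ | 0 | 0.8δ |

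The paired tests are distorted through the altered baseline in either case. The between-arm contrast loses only s = p × k.

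**3. Power against shrinkage s**

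The documents give a total of 40 patients and a 0.05 threshold. They give no allocation ratio, sidedness, effect size, SD, power or dropout rate, so there is no power figure to reproduce. Assumed: 20 per arm, two-sided 0.05, normal approximation, no dropout.

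- Standardised effect detectable with 80% power: (1.960 + 0.842) × √(2/20) = 2.802 × 0.3162 = 0.886
- Power after shrinkage: Φ(2.802 × (1 − s) − 1.960)
- Number per arm to restore 80%: 20 / (1 − s)², rounded up

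| s | Example (p, k) | 2.802(1 − s) − 1.960 | Power | Per arm to restore 80% |
|---|---|---|---|---|
| 0% | any p, k = 0 | 0.842 | 80.0% | 20 |
| 5% | 10%, one half | 0.702 | 75.9% | 23 |
| 10% | 20%, one half; or 10%, full | 0.562 | 71.3% | 25 |
| 20% | 20%, full | 0.282 | 61.1% | 32 |
| 30% | 30%, full | 0.001 | 50.0% | 41 |

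With the t distribution the detectable effect is 0.909 rather than 0.886, and the powers agree to within 0.1 percentage point.

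**The case against.** Much of the case on the other side stands.

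*The clause can be used at entry.* A reader might infer that a criterion about conduct during the study cannot be applied before randomisation. The same list excludes planned pregnancy, which is also forward-looking and is screened by asking about intent. Read that way, the clause keeps out current users who mean to continue. Those it leaves in are users who stop at entry.

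*No patient is removed.* A reader might infer that the rule drops randomised patients for later behaviour and so selects differently by arm. No section withdraws a patient for taking an outside probiotic, and the SAP's ITT set keeps such patients. What remains is that the handling is not reconciled between the two documents.

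*The study's own capsules are not caught.* The wording does not say non-study, but the protocol assigns the capsules shortly before the criteria. Reading the clause against them is strained.

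*The larger losses of power are extreme.* Shrinkage of 20% or 30% needs either a high share of users with full effect persisting six weeks after stopping, or a still higher share with partial carry-over. Recent users are balanced in expectation by randomisation, so the expected result is attenuation between arms and not a spurious between-arm difference. This is why the range starts at 0%.

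None of this supplies the missing look-back or protects the paired tests from an altered baseline.

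**Conclusion.** The point holds in two parts. First, no criterion bars probiotic use up to baseline sampling by patients who then stop. Such baselines can distort the within-group paired tests even when carry-over clears early. Second, the protocol and SAP leave the handling of outside use after randomisation unsettled. The documents do not support the stronger claims that the clause is unusable at entry or that it takes randomised patients out of the trial.

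The size is unknown, because the documents give neither the rate of probiotic use nor the duration of carry-over. Under the stated assumptions, power for the between-arm comparison lies between about 80% (no shrinkage) and 50% (30% shrinkage), and early clearance keeps it near the top of that range. The sponsor should make the change because it is cheap and protects the reference value of a planned analysis, not because a large loss has been shown.

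**What to change.** 1. Add an entry criterion: no non-study probiotic within a stated look-back before baseline sampling. The investigators set its length, as they did for the other treatments.
2. Change the existing phrase so that it refers to non-study probiotics.
3. Record non-study probiotic use after randomisation as a protocol deviation. State that the patient stays in ITT, and add this use to the SAP's per-protocol exclusions.
4. For patients already enrolled, run a sensitivity analysis without recent users, if the questionnaire recorded when probiotics were last taken. The visible text shows only that use was asked about, so check this first.

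The cost is one added criterion, one reworded phrase, one line in the SAP's per-protocol definition and possibly one sensitivity analysis. A few recent users would be delayed or not enrolled. Parts of the protocol and the whole SAP are in the past tense, so recruitment may be over. In that case item 1 cannot help this trial. Items 3 and 4 remain as far as the recorded data allow, and the missing look-back should be reported as a limitation.
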